### 5.6 Criteria for discontinuation

Any participants who meet any one of the following criteria at any point after enrollment will be discontinued from the study:

- Urgent need for a D&E
- Decision not to proceed with the D&E
- Decision to stop participation in the study

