### 5. Research design and General Methodological Approach

We have chosen a randomized controlled trial to ensure that neither patient nor provider will be biased by medication choice. Seventy-two English or Spanish-speaking women greater than 18 years of age and at 16 0/7-20 6/7 weeks gestation will be enrolled with 36 women in each arm.

Computer-generated randomization will be utilized to assign treatment arms and the vaginal misoprostol and buccal placebo and buccal misoprostol and vaginal misoprostol will be prepared according to randomization scheme by the research pharmacy in opaque-sealed envelopes as to blind participants and providers.

One arm will receive mifepristone 200mg orally 20–24 hours prior and misoprostol 400mcg (two 200mcg tablets) vaginally 1–2 hours prior and placebo (two lactose tablets designed to appear similar to misoprostol) buccally 1–2 hours prior to D&E. The second arm will receive mifepristone 200mg orally 20–24 hours prior and misoprostol 400mcg (two 200mcg tablets) buccally and placebo (two lactose tablets designed to appear similar to misoprostol) vaginally 1–2 hours prior to surgical abortion. The patients will place the tablets in the pre-operative area from pre-marked envelopes. The patient will be instructed to take the medication in the envelope marked buccally (misoprostol 400 mcg or placebo) to be placed in the cheek pouch for 30 minutes and then remaining swallowed and the envelope marked vaginally (misoprostol 400mcg or placebo) to be placed vaginally as far as the patient can insert with her finger. The patient will be witnessed taking the buccal medication but the patient will be given privacy for vaginal administration. The time will be recorded in the patient's chart. Prior to the procedure, patient assessment of medications will be obtained as detailed in 5.5.

At 1–2 hours after misoprostol and placebo administration, the participant will be brought into a procedure room for a dilation and evacuation (D&E). Prior to the D&E, an assessment of cervical dilation will be made as assessed by largest size Pratt dilator accepted without resistance starting with 39–French. Only the attending will assess cervical dilation but procedures will be performed by the attending and residents-in-training. Type of provider will be recorded.

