## 5.1 Criteria for selection of subjects

The trial will be conducted at Virginia Commonwealth University Medical Center (VCUHS) and Virginia League of Planned Parenthood (VLPP) over the course of approximately fourteen months. The study will enroll healthy women, over 18 years of age, eligible for non-urgent D&E at 16 0/7 weeks to 20 6/7 weeks gestation, confirmed by sonogram. Patients presenting to either office in consultation for a D&E will be recruited for participation. Exclusion criteria will include: emergent need for D&E, intrauterine infection, fetal demise, molar pregnancy, multiple pregnancy, uterine anomaly or significant distortion of the uterus with fibroids, intolerance, allergy or contraindication to mifepristone or misoprostol.

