### 5.4 Admission procedure

Recruitment will begin July 2015 and extend for approximately fourteen-months, ending once enrollment is complete. Patients presenting to VCUHS or VLPP will be enrolled, as described in 5.2. Following enrollment, the patient will complete an admission form including baseline demographics and reproductive history.

After ensuring the patient meets eligibility criteria, has signed consents and following the preoperative assessment, a research staff member will give the patient mifepristone 200mg to take orally in the staff member's presence and the time will be recorded in the patient's chart. The following day, a research assistant will dispense two numbered (one vaginal and one buccal) envelopes as described in 5.2 upon arrival to VCU Medical Center for the procedure. Prior to dispensing the envelope, the research staff member will examine the allocation numbers as recorded in the patient's chart to ensure a match.

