### 5.9 Data analysis

STATA statistical software (StataCorp LP, College Station, TX, www.stata.com) will be used to analyze the baseline characteristics of the populations based on the study questionnaires completed by participants prior to their procedure. Primary and secondary outcomes will be recorded as described above in 5.4. Both primary and secondary outcomes will be analyzed using t-tests or appropriate non-parametric comparison tests as appropriate. The perception assessments (VAS) will be assessed using non-parametric analysis. The primary analysis will be based on intention to treat.

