### 5.10 Number of subjects and statistical power

Sample size is based on prior studies assuming that longer procedure times reflect a need for further dilation and manipulation. Procedure time is defined in this study as first instrument passing into the uterus until last instrument out of the uterus. Previous studies have defined a 3-minute for 14-16 week gestations or 5-minute change for 19-24 week gestations as clinically significant. For this study evaluating 16 - 20 6/7 week gestations, we chose 4-minute difference as clinically significant. Using a superiority design, in order to detect a 4-minute change in procedure time from a baseline of 10 minutes with a standard deviation (SD) 5 minutes), with a two-tailed alpha of 0.05 and power of 90%, 33 women will be needed in each arm. We plan to recruit 72 participants due to post-enrollment exclusion.

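### Section 5.6 takes participants who need an urgent D&E out of the study even after the randomised tablets, and nothing keeps their procedure times for the intention-to-treat analysis in 5.9

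*Combined protocol and SAP*

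**What the plan says.** - **Entry (5.1).** "Exclusion criteria will include: emergent need for D&E". This applies before enrollment and is not in dispute.
- **Discontinuation (5.6).** "Any participants who meet any one of the following criteria at any point after enrollment will be discontinued from the study". The first criterion listed is "Urgent need for a D&E"; the others are deciding against the procedure and deciding to leave the study. The exit is from the study, not only from study treatment.
- **Timing (5, 5.4).** Mifepristone is the same in both arms and is given the day before. The randomised tablets come on the procedure day: "The following day, a research assistant will dispense two numbered" envelopes, and "The patients will place the tablets in the pre-operative area from pre-marked envelopes". The D&E follows 1–2 hours later.
- **Primary outcome (5.10).** Time from the first instrument entering the uterus to the last one leaving it.
- **Analysis (5.9).** "The primary analysis will be based on intention to treat". The section defines no analysis set and has no rule for data after discontinuation.
- **Sample size (5.10).** "We plan to recruit 72 participants due to post-enrollment exclusion". The abstract attributes the extra recruitment to dropout or disqualification.

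**The concern.** An exclusion that is harmless at entry is carried forward past randomised treatment. Of the three criteria in 5.6, the urgent D&E is the one that matters here. A participant who decides against the procedure has no procedure time, and one who withdraws has made her own choice. A participant who becomes urgent after the tablets still has a D&E, and it can be timed.

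The trial's hypothesis (section 2) is that route changes the effect on the cervix, so urgent need after dosing could differ by arm. Removing such participants would then make the arms differ in who is left. This is the kind of loss that intention to treat is meant to prevent. It also cannot be repaired later: section 9 completes data collection on the day of the procedure, so a time that staff did not record because the participant was considered out of the study is gone.

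**Working it through.** **1. The plan's own figure.** Inputs from 5.10: difference 4 min, SD 5 min, two-sided alpha 0.05, power 90%.

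n per arm = 2 × [SD × (z₀.₉₇₅ + z₀.₉₀) / difference]² = 2 × [5 × (1.960 + 1.282) / 4]² = 32.84, rounded up to 33.

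The stated 33 per arm reproduces. The sample size is not in question.

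**2. When a loss can depend on arm.**

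| Period | Can the randomised tablets cause the loss? | Can a procedure time exist? |
|---|---|---|
| Enrollment and mifepristone, up to the tablets | No: same drug in both arms, tablets not yet taken | If a D&E is done |
| Tablets to D&E, 1–2 hours | Yes | Yes, if a D&E is done |

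Only the second row raises the possibility of bias by route. The rule in 5.6 covers both.

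**3. Loss of numbers alone.** Noncentral-t power is 91.7% with 36 v 36, 91.4% with 35 v 36 and 91.0% with 34 v 36. Losing one or two participants costs less than one point. What matters is which participants are lost.

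**4. Simple size of the shift.** If k of 36 are dropped from one arm and their times differ on average by 5 min (one SD, assumed) from those kept, the arm mean moves by k/36 × 5: 0.14 min for k = 1, 0.28 for k = 2 and 0.42 for k = 3, against the 4-minute target.

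**5. Simulation, illustration only.** Assumptions: 36 per arm, gamma times with SD 5, pooled t-test, losses in one arm only. With no true difference both means are 10 (shape (10/5)² = 4, scale 25/10 = 2.5). Bias is the arm with losses minus the other arm.

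| Lost from one arm | Fastest lost: bias, type I error | Slowest lost: bias, type I error |
|---|---|---|
| 1 | +0.21 min, 5.7% | −0.39 min, 6.9% |
| 2 | +0.41 min, 7.2% | −0.69 min, 10.3% |
| 3 | +0.61 min, 9.1% | −0.96 min, 14.9% |

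The two directions are not mirror images, because procedure times are skewed to the right. Milder selection gives less: one or two lost at random from the fastest 12 gives +0.13 or +0.28 min, with type I error of 5.1% or 5.7%. Losses at random from all 36 give no bias and type I error of about 5%.

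**6. Power under the same assumptions, means 10 v 6.** With no loss, power is 90.5%. Losing the one or two fastest from the faster arm gives 88% or 85%. Losing them from the slower arm gives 93% or 94%. Losing them equally from both arms leaves about 90%.

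**7. How many losses.** The documents give no rate. At an assumed 1% to 5% urgent need after dosing, the expected number per arm is 36 × 0.01 = 0.36 to 36 × 0.05 = 1.8. This is why one or two is the case to look at.

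**The case against.** The strongest reply is that the sections do not contradict each other. Section 5.6 ends participation and says nothing about analysis, while 5.9 is the only analysis rule and it says intention to treat. If the time is recorded, both can be followed. The exclusions foreseen in 5.10 may be losses in the day after mifepristone, before any randomised tablet. The window that can depend on arm is 1–2 hours on site. Section 3 links the high expulsion risk in earlier work mainly to a 48-hour interval between the drugs, which this trial does not use.

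Much of this stands. A reader might infer that the plan excludes these participants from the analysis; it does not say so. A reader might also infer a known bias, or a loss of power. The documents support neither, because they do not say how often urgent need would arise, in which arm, or whether those procedures would be fast or slow.

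What does not stand is that 5.9 settles the matter. An analysis rule cannot use a time that was never recorded, and the instruction staff will follow on the day is the one in 5.6.

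**Conclusion.** The concern holds as a gap between 5.6, 5.9 and 5.10 that should be closed. Read literally, 5.6 can drop a measurable primary outcome after randomised dosing, for a reason that may depend on route, and no section prevents it.

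The effect is probably small. With one or two extreme cases lost from one arm, the illustrative bias is 0.2–0.4 min if they are the fastest and 0.4–0.7 min the other way if they are the slowest. Type I error is about 6–7% and 7–10% respectively, and power may fall or rise. These figures rest on assumed numbers of losses, one-sided loss, extreme cases and gamma times. They are neither forecasts nor bounds. If the losses are unrelated to response, there is no bias. The case for changing the text is that the correction costs almost nothing and the lost data cannot be recovered.

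**What to change.** Leave the clinical criteria as they are and change only what happens to the data.

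1. **5.6:** state that, once a participant is allocated, meeting a discontinuation criterion does not end data collection. Procedure time is recorded for any D&E performed. Other outcomes, such as the dilator assessment and the patient survey, are recorded where feasible without delaying or altering care. Both apply unless consent is withdrawn.
2. **5.9:** state that all allocated participants with a procedure time are analysed in their allocated arm. Those without one (no D&E, expulsion, withdrawal) are reported by arm, timing and reason.
3. **5.10:** state that exclusion after enrollment means losses before allocation, or participants with no procedure time. It does not mean removing allocated participants who have one.

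The rule should start at allocation, not at dispensing. Section 5.2 assigns the envelope once eligibility is confirmed, and 5.4 has staff check it against allocation numbers already in the chart, whereas section 9 places allocation on the procedure day. If allocation comes first, an analysis set that began at dispensing would itself allow exclusions after randomisation.

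Cost: a few sentences, with no added participants, visits or staff. The downside is that times from urgent procedures may be harder to record and may add some noise. Participants with no procedure time still cannot enter the procedure-time test, so reporting them by arm is the most that can be done.

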### 5.7 Data management

Data will be entered by the research coordinator and stored on a computer at each center accessible only to the primary and co-investigators and research coordinator via password protection.

### 5.9 Data analysis

STATA statistical software (StataCorp LP, College Station, TX, www.stata.com) will be used to analyze the baseline characteristics of the populations based on the study questionnaires completed by participants prior to their procedure. Primary and secondary outcomes will be recorded as described above in 5.4. Both primary and secondary outcomes will be analyzed using t-tests or appropriate non-parametric comparison tests as appropriate. The perception assessments (VAS) will be assessed using non-parametric analysis. The primary analysis will be based on intention to treat.

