## 5.2 Subject recruitment and allocation

Both VCUHS and VLPP serve representative samples of Richmond, Virginia. Second trimester services at VLPP started in 03/2014.

After the patient has completed the counseling process and decided to proceed with an induced abortion, she will be approached by either a co-investigator or research staff member and asked to participate in the study. A detailed explanation of the study will be provided and informed consent obtained in English or Spanish, according to patient preference. A copy of the informed consent will be given to the patient. Eligibility for the study will be confirmed.

The VCU Investigational Research pharmacy will prepare the allocation sequence for preparation of allocation envelopes. Subjects will be allocated in blocks of 4–6. A researcher not involved in subject recruitment and without participant contact will prepare sequentially numbered opaque envelopes with the assigned, blinded pills for vaginal or buccal administration (misoprostol or placebo) enclosed. The envelope will not contain information that would reveal the group assignment. The envelope will not be assigned to a participant until eligibility is confirmed. The envelope will not be opened until just prior buccal and vaginal placement. The allocation number will be recorded twice in the participant's chart. The envelope will be attached to the chart. The envelope will only have the allocation number on the outside and the blinded pills inside.

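### Optional gain in precision: procedure time is compared without adjustment, although gestational age is known for every woman before allocation

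*Combined protocol and SAP*

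**What the plan says.** Section 5.9 is the whole analysis plan. It states: "Both primary and secondary outcomes will be analyzed using t-tests or appropriate non-parametric comparison tests as appropriate", and adds: "The primary analysis will be based on intention to treat". Neither it nor any other section names a covariate or a regression model.

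Section 5.1 admits women "eligible for non-urgent D&E at 16 0/7 weeks to 20 6/7 weeks gestation, confirmed by sonogram". Section 5.2 fixes the order of events: "The envelope will not be assigned to a participant until eligibility is confirmed". On randomisation, 5.2 says: "Subjects will be allocated in blocks of 4–6", and names no stratification factor.

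Section 5.10 uses gestation to set the target difference: "Previous studies have defined a 3-minute for 14-16 week gestations or 5-minute change for 19-24 week gestations as clinically significant". It then chooses 4 minutes for the range between. The sample size is calculated "in order to detect a 4-minute change in procedure time from a baseline of 10 minutes with a standard deviation (SD) 5 minutes", with 90% power, two-sided alpha 0.05 and 33 women per arm.

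**The concern.** Gestational age meets the usual conditions for a baseline covariate. It is measured before allocation, the route of misoprostol cannot affect it, and it is required for eligibility, so no woman should lack it. The plan uses it to limit entry and to choose the target difference, but neither the allocation nor the analysis takes account of it.

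In an unadjusted comparison, any variation in procedure time that follows gestation stays in the error term. With about 33 women per arm, a related covariate would narrow the confidence interval and raise power without new data. Allocation is not stratified, so the arms may also differ in gestation by chance. A covariate named in advance deals with that without a model chosen after the results are seen.

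**Working it through.** **Inputs.** From 5.10: difference 4 minutes, SD 5, two-sided alpha 0.05, power 90%, 33 per arm. From 5.1: a window of 16 0/7 to 20 6/7 weeks, which is 35 possible days and 34 days from first to last. Assumed, because the documents give no value: R², the share of within-arm variance in procedure time that gestation explains.

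**Step 1: the plan's own figure.** n per arm = 2(1.960 + 1.282)² × 25/16 = 32.8, so 33. The stated size reproduces for the unadjusted comparison.

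**Step 2: unadjusted power.** SE = 5 × √(2/33) = 1.231 minutes on 64 df. The noncentral t distribution gives 89.3% power. The 95% CI half-width is 1.998 × 1.231 = 2.46 minutes.

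**Step 3: power with one covariate.** The variance of the adjusted difference is 25(1 − R²)(2/33)[1 + 1/(66 − 3 − 1)] on 63 df. The bracket, 1 + 1/62 = 1.016, is the expected price of chance imbalance in the covariate.

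| R² (assumed) | SE (min) | CI half-width (min) | Power |
|---|---|---|---|
| unadjusted | 1.231 | 2.46 | 89.3% |
| 0 | 1.241 | 2.48 | 88.8% |
| 0.05 | 1.209 | 2.42 | 90.3% |
| 0.10 | 1.177 | 2.35 | 91.7% |
| 0.30 | 1.038 | 2.07 | 96.7% |

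**Step 4: break-even.** Adjustment pays once (1 − R²) × 1.016 falls below 1, which is R² of about 0.016. Allowing for the lost degree of freedom leaves it at 0.016.

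**Step 5: what each R² means in minutes.** If gestation is spread evenly over 35 days, its variance is (35² − 1)/12 = 102 days², or 102/49 = 2.08 weeks². The slope is √(R² × 25/2.08) minutes per week, and the rise over the window is the slope × 34/7.

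| R² | Slope (min per week) | Rise over the window (min) |
|---|---|---|
| 0.016 | 0.44 | 2.2 |
| 0.05 | 0.77 | 3.8 |
| 0.10 | 1.10 | 5.3 |
| 0.30 | 1.90 | 9.2 |

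An R² of 0.10 already needs a rise larger than the 4-minute target. An R² of 0.30 needs a rise close to the whole 10-minute baseline mean, so that row is an upper bound. If enrolment clusters in a few weeks, the same slope gives a smaller R².

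**The case against.** The strongest reply is that nothing is broken. Design and analysis agree, since the sample size was calculated for the unadjusted comparison that 5.9 plans. No stratification factor is named, so none is left out of the analysis. That stands, and it is why this is only an optional improvement.

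Second, the benefit depends on an R² that the documents do not supply. A reader might take the 3- and 5-minute figures in 5.10 as evidence that procedures lengthen with gestation. They are differences judged clinically significant, not mean times, and give neither a slope nor a correlation. At R² of 0.05 the gain is 1.0 point of power and 0.04 minute of half-width. This also stands.

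Third, the scale of analysis can matter more than adjustment. In simulations with assumed lognormal times (means 10 and 14, SD 5), the adjusted minutes model had 88% to 91% power at R² up to 0.10, against about 95% for the plain rank test that 5.9 already allows. So adjustment does not make up for a poor scale. The choice of scale is a separate matter, and this point takes no position on it.

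What remains is the asymmetry: a known, small loss if gestation is irrelevant, against a gain at any R² above about 0.016.

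**Conclusion.** The point holds as an optional efficiency gain. Section 5.9 leaves unused a baseline value that exists for every woman before allocation. At the planning figures, adjustment changes power by −0.5 point at R² = 0 (89.3% to 88.8%), +1.0 at 0.05 and +2.4 at 0.10. The result rests on an assumed R², roughly normal errors, a linear effect of gestation, a within-arm SD of 5 and 33 analysed women per arm. The minutes-per-week figures also assume an even spread of gestation.

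A reader might infer that the unadjusted test is biased, that the trial is underpowered without adjustment, or that 96.7% power is within reach. The documents support none of these. The comparison is randomised and the planned tests are valid. The 33 per arm reproduces; 89.3% rather than 90% is only the difference between the t distribution and the normal approximation. The 96.7% needs a rise of about 9 minutes across the window, for which the documents give no evidence.

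**What to change.** In 5.9, state that the primary comparison of procedure time, on whichever scale the sponsor fixes before unblinding, is adjusted for gestational age in days at the eligibility sonogram, as one continuous covariate.

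- On the minutes scale: a linear regression of procedure time on arm and gestational age. Report the adjusted mean difference with its 95% CI against the 4-minute target.
- If a rank test is chosen: a regression of the ranks of procedure time on arm and gestational age.
- Keep the planned unadjusted t-test or rank test as a sensitivity analysis.

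Operator type should not be added as things stand. Section 5 says "Type of provider will be recorded" but not when it is determined, so it cannot be assumed to precede study drug.

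The cost is a few lines of text and no new measurement or change in sample size. The statistical cost is about half a point of power if gestation is unrelated to procedure time.
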